## EMPOWER-II

diagnosed with cancer who survived five or more years from diagnosis. Participants will be recruited in three waves (97/wave) by the CCSS Coordinating Center, which has extensive experience recruiting for our studies. We anticipate enrolling 97 participants in Year 1 and then the remaining 194 in Year 2. All eligible members of the CCSS cohort will be identified by the CCSS Statistical Center. We will randomly sample CCSS members from this eligibility list to contact regarding participation in this study.

An introductory letter of invitation will be sent via e-mail by the CCSS Coordinating Center. Included in this e-mail will be (1) an invitation to join the EMPOWER-II study; (2) instructions on how to download the Eureka platform and (3) a brief summary of study activities. A second letter will be sent to non-responders via regular mail. After 3 weeks, a telephone interviewer from the CCSS Coordinating Center will then call potentially eligible cohort members who fail to respond to 2 invitation letters and invite them to participate. After 3 weeks, a final invitation letter will be sent via regular mail. Once interested participants have downloaded the Eureka app, they will receive push notifications leading them to an FAQ sheet and eligibility checklist within the app. Eligible participants will then receive an electronic consent form via the app along with a HIPAA waiver, and a link to the privacy policy of Eureka. We will continue attempting to accrue subjects from the eligibility list until 320 members have been randomized in the study. With over 1,400 women in the CCSS potentially eligible for this study and the high participation rate in EMPOWER-I, we do not anticipate a problem in enrolling 320 participants. During the study enrollment, there will be an estimated 1,456 women who fulfill the eligibility criteria.

All participating survivors will be compensated \$50 for each survey completed at baseline and at the end of the study (\$100 total for each survivor). We will also compensate PCPs for their time in answering the short survey at baseline and at the end of the study. We will compensate at the same rate as the survivor participants: \$50 per survey (\$100 total for each PCP).

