### 3.2 Randomization and Stratification

After completion of the baseline questionnaire, participants will be randomly assigned, in a ratio of 1:1:1, to one of the three groups (control, PA, PA+PCP). Randomization will be stratified by age at study enrollment (25-39,  $\geq 40$ ), by cancer diagnosis (Hodgkin lymphoma, other cancers), and by receipt of a previous breast imaging exam (either mammogram or breast MRI) in the previous 24 months (yes, no). Because we did not observe a difference in mammography or breast MRI surveillance between white, non-Hispanic and minority survivors in EMPOWER-I, we will not stratify by race/ethnicity. However, we will oversample from minorities in CCSS with the goal of having 18% of participants in the trial coming from minority populations. Further, since only a small percent of participants had a family history of breast cancer (<1%) or did not have a PCP (8%), we will not stratify by these two factors. However, we will have tailored push notifications / video vignettes for women without a PCP that are intended to help them find one. These three stratification factors were chosen because of the desire to maintain balance between the three arms with respect to age, cancer diagnosis, and recent single imaging study while simultaneously keeping the number of strata to a minimum and ensuring stratum size does not get too small. We will use a permuted block randomization scheme with a block size of three and six. A computer-based random number generator will be used to generate the sequence of assignments in advance.

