### 6.2 Sample Size and Power

The primary aim involves two pair-wise comparisons of equal importance. For each comparison, we fix the probability of a Type I error at 0.025 in order to maintain the overall probability of a Type I error at 0.05. We powered the study to detect a difference of 20% for each pair-wise comparison assuming equal randomization to each of the three arms and that the proportion of women in the control group who will have a mammogram and an MRI will be approximately 10% based on our previous work. Table 1 shows the power we expect to have using two-sided Mantel-Haenszel tests and indicates that we should have sufficient power to detect a clinically meaningful difference even if the proportion of women in the control arm with the primary endpoint is somewhat higher than we expect. The power calculation of the Cochran-Mantel-Haenszel tests assumes a common risk ratio among the strata, that all strata generate the same proportion for the control arm and intervention arm.

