**Table 1. Power to detect a difference between an intervention and control arm**

Proportion with mammogram and MRI in the control arm	Proportion with mammogram and MRI in an intervention arm	Difference	Power among all participants
10%	28%	18%	83%
10%	30%	20%	90%
15%	35%	20%	80%

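### Table 1's 80% power for 15% versus 35% does not share the basis that gives its other two rows, and the wave and year counts in section 3.0 total 291 against a target of 320

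*Combined protocol and SAP*

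**What the plan says.** Section 6.2 sets the inputs for the two primary comparisons: "For each comparison, we fix the probability of a Type I error at 0.025", two-sided Mantel-Haenszel tests, equal arms, a control rate of about 10% and a target difference of 20 points. It assumes the same proportions in every stratum. It then states that "Table 1 shows the power we expect to have using two-sided Mantel-Haenszel tests and indicates that we should have sufficient power". Under the column heading "Power among all participants", Table 1 prints:

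- 10% v 28%: 83%
- 10% v 30%: 90%
- 15% v 35%: 80%

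The section relies on the last row when it says that power is adequate "even if the proportion of women in the control arm with the primary endpoint is somewhat higher than we expect". It gives no n per arm and does not say whether a continuity correction was applied.

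The sample size has to be taken from section 3.0. That section opens with a target of 320 and continues accrual "until 320 members have been randomized in the study"; Appendix IV also gives 320. Section 3.2 says that "participants will be randomly assigned, in a ratio of 1:1:1, to one of the three groups (control, PA, PA+PCP"), so 320 means 106 or 107 per arm. Yet section 3.0 also says "Participants will be recruited in three waves (97/wave) by the CCSS Coordinating Center", and then "We anticipate enrolling 97 participants in Year 1 and then the remaining 194 in Year 2".

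**The concern.** Two of Table 1's rows have the same 20-point difference, and the first has 18 points at a lower control rate. Under ordinary two-proportion methods, 10% v 28% and 15% v 35% have almost equal power, yet the table puts the second 3 points below the first. That suggests that the third figure comes from a different n or a different test variant.

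The third row is the one offered as protection against a higher control rate than expected, so a reader should be able to reproduce it. With n missing from section 6.2, the reader turns to section 3.0 and finds counts that imply both 291 and 320.

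**Working it through.** **Inputs.** Two-sided alpha 0.025 gives z = 2.2414. Arms are equal. The rates are those of Table 1, first taken as exact. Because section 6.2 assumes identical proportions in all strata, an unstratified two-proportion calculation is a fair check. Candidate sizes are 291/3 = 97 and 320/3 = 106.67 per arm.

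**Formula.** With d = p2 − p1 and p̄ = (p1 + p2)/2:

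Power = Φ{[d − c − z·√(2p̄(1−p̄)/n)] / √([p1(1−p1) + p2(1−p2)]/n)}

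where c = 0 (uncorrected, pooled null variance) or c = 1/n (continuity-corrected).

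**Reproducing row 1 (10% v 28%) at n = 97, uncorrected.** The null SE is √(0.3078/97) = 0.0563 and the alternative SE is √(0.2916/97) = 0.0548. Then (0.18 − 2.2414 × 0.0563)/0.0548 = 0.980, so power is 83.6%. This is within a point of the printed 83%.

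**Row 3 (15% v 35%) on the same basis.** The null SE is √(0.375/97) = 0.0622 and the alternative SE is √(0.355/97) = 0.0605. Then (0.20 − 2.2414 × 0.0622)/0.0605 = 1.002, so power is 84.2%. With c = 1/97 = 0.0103 the deviate falls to 0.832 and power to 79.7%.

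**All rows:**

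| Basis | 10 v 28 | 10 v 30 | 15 v 35 |
|---|---|---|---|
| Printed | 83 | 90 | 80 |
| 97 per arm, uncorrected | 83.6 | 90.0 | 84.2 |
| 97 per arm, corrected | 78.6 | 86.3 | 79.7 |
| 320/3 per arm, uncorrected | 87.3 | 92.7 | 87.8 |
| 320/3 per arm, corrected | 83.2 | 90.0 | 84.1 |

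Rows 1 and 2 agree with each other on two bases, and row 3 is about 84% on both. The printed 80% fits 97 per arm with correction, where rows 1 and 2 would be 78.6% and 86.3%.

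**Rounding of the power column only.** The n per arm at which each row rounds to its printed power is:

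- uncorrected: 94.3-96.6, 95.5-98.6 and 86.8-88.8
- corrected: 105.1-107.5, 105.3-108.4 and 96.6-98.6

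Row 3's range does not meet the other two in either case. The same holds for the unpooled, arcsine, log risk ratio and log odds ratio formulas.

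**Ordering.** Nine methods were tried at 80 to 120 per arm: these six formulas plus exact calculations for the Mantel-Haenszel test with and without correction and for Fisher's test. Row 3 minus row 1 ran from −0.5 to +2.0 points. Table 1 prints −3, and rounding of the two powers allows −2 to −4.

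**Rounding of the rates as well.** Let each rate and each difference vary within half a point of its printed value. All three printed powers can then be had at one n: about 92 per arm uncorrected or 102 corrected. At the two sizes in the documents they cannot:

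- The least favourable values for row 3 are 15.5% v 35.0%. They give 81.8% at 97 uncorrected and 81.6% at 320/3 corrected, about 82% and not 80%. Uncorrected power at 320/3 is higher still.
- The most favourable values for row 2 are 9.5% v 30.0%. They give 88.6% at 97 corrected, not 90%.

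**Counts.** 3 × 97 = 291 and 97 + 194 = 291. The target is 320, and 320 − 291 = 29.

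**The case against.** The best defence is that little depends on this. One cell of three is off, by about 4 points, and at 320 it errs on the cautious side. Alpha, test, endpoint, analysis set and target are untouched. The document also appears to postdate recruitment planning: section 4.0 refers to a COVID recruitment hold and to 63 participants already well past the 18-month window. All of that stands, and it limits the weight of the point.

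Four stronger readings are tempting, and the documents do not support them.

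- **That recruitment will end 29 women short.** Section 3.0 continues accrual until 320 are randomized. The 97s are wave sizes and a forecast.
- **That none of Table 1 can be reproduced at the target.** Rows 1 and 2 do reproduce at 320 with a continuity correction; only row 3 fails.
- **That no n whatever fits the table.** This is true only if the printed rates are exact. With rounding allowed, about 92 or 102 per arm would do, although neither size appears in the documents and the rates look like chosen scenario values.
- **That the table mixes 320 and 291.** With correction, rows 1 and 2 fit the first size and row 3 the second. That pattern is suggestive, but nothing in the text confirms it.

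An unstated alpha does not resolve the table either. For example, 0.0125 at 107 per arm, uncorrected, gives 81.1/88.4/81.7%. That comes within 2 points of every row, but only by missing rows in opposite directions.

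**Conclusion.** The concern holds as an internal inconsistency of minor weight. At two-sided alpha 0.025, the 15% v 35% power is about 84% on either basis that recovers the other two rows, against 80% printed. The size of that gap assumes that the printed rates are exact; the failure to fit at 97 or 106-107 per arm remains when they are allowed to be rounded. The documents do not show which row is wrong, because n and the correction are not stated.

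The mismatch of 291 and 320 is plain arithmetic and needs no assumption. It is a contradiction in planned counts only.

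A reader might infer that the trial is underpowered at a 15% control rate. It is not, under the plan's own rates: at 320 the nine methods give 83-89% for that row and at least 81% for every row. Section 6.2's conclusion of sufficient power is therefore not overturned.

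**What to change.** In section 6.2, recompute all three rows of Table 1 on one basis at 320 randomized (106-107 per arm) and two-sided alpha 0.025. State the n per arm and whether a continuity correction is used. The rows would read about 87/93/88% uncorrected with pooled variance, or about 83/90/84% with correction.

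In section 3.0, reconcile the wave and year counts with 320, or delete them if they no longer describe accrual.

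The cost is one recomputed table, one added sentence and two edited or removed counts. No extra participants are needed, and the endpoint, alpha, test, analysis set and target do not change.

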**Table 1. Power to detect a difference between an intervention and control arm**

Proportion with mammogram and MRI in the control arm	Proportion with mammogram and MRI in an intervention arm	Difference	Power among all participants
10%	28%	18%	83%
10%	30%	20%	90%
15%	35%	20%	80%

### Supplemental Imaging

To inform our power calculations, we used density measures reported on the outside radiology reports for women in EMPOWER-I and then used three different proportions of BI-RADS 3/4 density: 0.60, 0.65, 0.70. We then used the age-appropriate breast density proportions reported by the Breast Cancer Surveillance Consortium (<http://tools.bscs-scc.org/dataexplorer/>) as shown in Table 2. We will use a 1:3 matched non-cancer population for comparison.

## EMPOWER-II

**Table 2. Power to detect a difference between the two populations.**

	EMPOWER (N=102)	Breast Cancer Surveillance Consortium (N=1,072,517)	Delta	POWER
Scenario I	0.60	0.54	0.06	0.21
Scenario II	0.65	0.54	0.11	0.57
Scenario III	0.70	0.54	0.16	0.89

As noted above, we will use a 1:3 matched non-cancer population for comparison. Of note, the sample above is based on our estimates of mammograms we will obtain during the proposed funding period. As noted, after the funding period, we will continue to collect breast imaging studies among women in EMPOWER-II, thus increasing the potential power of the analysis.

Using Cumulus, the measured percent mammographic density is a continuous number and will be summarized using descriptive statistics such as the mean, median, and range. Summaries may be presented by age at exam, menopausal status, age at childhood cancer diagnosis, and time from cancer diagnosis. Analyses will proceed as described for BI-RADS density using models adjusted for the matching factors (age at study, calendar year of study, race/ethnicity, menopausal status).

## 7.0 Data Storage and Confidentiality

All information will be labeled with unique study identification numbers and stored in password-protected computerized databases. Study files will be kept in locked cabinets and access restricted to study staff. No data will be sent over the internet unless it is encrypted. Only key personnel will have access to the information in the database on an as-needed basis. Key personnel may not alter the data in the database or directly view all of it without specific cause and approval of the PIs. All email with subject-identifiable information will be encrypted. Findings will be presented in aggregate form only, with no references made to the individual participant's data. Confidentiality of each participant's data will be protected with utmost care with all questionnaire data identified solely by a code number. A list matching participant's names and code numbers will be maintained on a separate sheet of paper kept in locked storage at the CCSS Coordinating Center.

### At Duke

All staff members will be informed prior to employment and at regular intervals as to the necessity for keeping all data confidential. All written study material will be stored in locked file cabinets. Any identifying data will be kept on the Duke Cancer Institute server and each staff member's PC will be password protected. The names, geographic designation, and contact information for participants and their primary care providers will be sent to Duke staff via data reports through the Eureka platform and stored in the Duke server.

### Supplemental Imaging

Data will be entered into the Duke EMPOWER database. The images will be stored in Digital Imaging and Communications in Medicine (DICOM) format, transmitted to a Picture Archiving and Communications System (PACS) reading station for review and retrieval, and permanently and securely archived in the Computational Environment for Radiological Research which is housed on a secure institutional server.

## 8.0 Data and Safety Monitoring

This protocol presents no greater than minimal risk to the subjects and adverse events are not anticipated. The entire Data and Safety Monitoring Plan for the study can be found in **Appendix IV**. All study staff at Duke University, Memorial Sloan Kettering Cancer Center, and St. Jude Children's Research Hospital will be thoroughly trained in the methods for identifying when an unanticipated problem or adverse event occurs and how to complete forms to report the event. All unanticipated problems and adverse events will be reported to the Principle Investigators, Drs. [name] and [name], who will report them to the IRB as soon as possible and within the following time frames: 1) report any death and potentially life-threatening events within 3 days of

## EMPOWER-II

notification of the event, 2) report any serious/unexpected adverse events associated with the study within 3 working days, 3) all other adverse events will be reported within 15 calendar days, 4) discuss any event that does not meet the above requirements with the study team and report yearly to the Duke IRB. This data will be reported to the DSMB for independent assessment.

### **Appendix I: Overview of Study Arms and Mediating/Moderating Variables**

#### **Content and Mediating / Moderating Variables Addressed for each group**

Group	Intervention	Content	Mediating / Moderating Variables Addressed
Control (C)	Mailed targeted print materials	
 
Survivorship Care Plan: individual cancer treatment summary, screening recommendations, and risk-reducing interventions to maintain health after treatment for childhood cancer
 
One-page description of the potential benefits and other considerations of breast cancer screening for women with a similar cancer history
 
A PopSocket with the EMPOWER logo. This is a convenient reminder method to keep participants engaged.
 
How to find a PCP
 
List of low cost options for mammography / breast MRI
 
A template of a letter that can be used, if needed, to obtain approval for coverage of a breast MRI from an insurance company
 
	
 
Knowledge / awareness
 
Risk perception
 
Barriers reduction
 

C + Patient Activation (PA)	Smartphone-based	
 
Push notifications and app messages are tailored in content and timing. See Appendix II for details.
 
Culturally tailored video vignettes (90 seconds each) will supplement several of the push notifications and app messages and include the following: 
 
i) How to find a PCP (applicable only for women without a PCP)
 
ii) How and why to talk to your provider about breast cancer screening with breast MRI / mammography
 
iii) Cost of breast MRI (finding low cost options and insurance letter templates for the PCP)
 
iv) Focus on importance of screening and ways to make it a priority
 
v) Why screening is important even in the absence of symptoms or breast problems
 
 
 
CCSS app will include an electronic version of the mailed targeted print materials.
 
	
 
Patient Activation: 
 
- Knowledge / awareness
 
- Self-efficacy to talk to PCP about breast cancer screening
 
- Active role in early detection
 
- Taking action
 
 
 
Risk perception
 
Barriers reduction
 
Affect
 
Health beliefs
 

C+PA+PCP Activation	Faxed materials from Duke to	
 
Cover letter with patient's name, history of chest RT, and recommendation for breast MRI and mammography (with source information) and contact information
 
	
 
Knowledge of risk and surveillance recommendations
 

## EMPOWER-II

(PA+PCP)	PCP office manager	
 
• Executive summary – breast cancer in childhood cancer survivors treated with chest RT and current breast cancer surveillance recommendations
 
• FAQ (one-page) discussing common questions, e.g., “why both a breast MRI and mammogram are recommended”, “my patient has dense breast tissue”, “what about radiation exposure from mammograms”, and “cost of imaging”
 
• Template of letter for insurance company for pre-authorization (if needed) of a breast MRI with the key words for insurance carriers and the ICD10 codes
 
	
 
• Barriers reduction with language for insurance company coverage and ICD10 codes
 
• Self-efficacy to answer patient questions about surveillance
 

-----------------	--------------------	---	---

### ***Appendix II: Intervention Components***

#### **Control (C) Group:**

The control group will only receive the print materials. We will use the core component of the EMPOWER-I intervention. Targeted print materials will be sent to women in all three groups (C, PA, PA+PCP) by 2-day express mail and by email and will include the items listed in ***Appendix I***. A Survivorship Care Plan will be included in all the targeted print materials. Based upon input from our Patient Advisory Board, we have changed the laminated card to a PopSocket and added an information sheet to find a PCP (if the participant does not have one). In addition, the information on low cost mammograms and breast MRI will include a link to the MRI Assistance Program (<http://www.rightactionforwomen.org/assistance/>) and the information on low cost mammography that was used in EMPOWER-I. All women enrolled in EMPOWER-II who meet the financial criteria for assistance (income below 400% National Poverty Level) will be eligible for assistance. For purposes of the non-profit status of RAW, women need to submit either the previous year's tax return or, if applicable, a copy of a Medicaid letter. Once these steps are completed, the participant's PCP can then order a breast MRI that is scheduled by DiagnosticWorks at one of their sites across the U.S. This step is not necessary in Canada, where a PCP can order a breast MRI for this high-risk population and have it covered by insurance.

#### **Patient Activation (PA) Group:**

Building upon the core intervention components used in EMPOWER-I (i.e., print educational materials), we will evaluate the utility of patient activation through use of automated, highly tailored and interactive push notifications, supplemented by linked 90-second video vignettes and mapped to the behaviors being encouraged, and a survivorship-specific smartphone app (Eureka app). The push notifications are built to work in concert with the Eureka app and do not require the app to be open to receive push notifications. Opening the push notifications will trigger study-related activities within the Eureka app. We will use the Eureka mHealth Research Platform for sending push notifications, brief surveys for updating information, video vignettes, and study activity reminders. The mHealth Research Platform Resource is a mobilized cohort and infrastructure to carry out clinical research studies using mobile and digital technology developed by the University of California, San Francisco (UCSF). The goal of the Resource is to provide an infrastructure for efficient data collection, storage, and sharing that can be configured to support internet- or mobile phone app-based research studies. Eureka supports data collection for consenting participants on behalf of IRB-approved research studies, stores that data on secure cloud-based servers, and provides access to that data to platform users (including

